## 12.6 Safety Analyses

The safety endpoints are:

- Adverse events including secondary surgical intervention (SSI)
- Device deficiencies
- Posterior capsular opacification
- Posterior capsulotomy
- IOL position change (tilt and decentration)
- Intraocular pressure
- Surgical problems
- Slit Lamp Examination
- Dilated Fundus Examination
- IOL Observations

Patient listings will be provided for adverse experiences occurred from informed consent to exposure to the test article. Safety variables above will be analyzed using Treatment-Emergent Safety Analysis Set. For continuous variables, descriptive statistics (mean, standard deviation, N, median, min and max) will be provided for actual value and change from baseline at each visit. For categorical variables, N and percent will be provided for each category at each visit.

## 12.7 Interim Analyses and Reporting

No interim analysis is planned.

## 12.8 Sample Size Justification

To enroll more than or equal to 30 eligible T2 eyes used for analysis, at least 30 subjects will be evaluated by a new Alcon Toric calculator that incorporates ocular trends in Toric IOL planning and unilaterally or bilaterally implanted with the AcrySof IQ PanOptix IOL (TFNT20).

Using a new Alcon calculator that incorporates ocular trends in Toric IOL planning, percentage of eyes with  $\leq 0.25$  D refractive cylinder at Visit 3/3A (Day 30-60) in T2 group was estimated as 60.9% based on a previous [REDACTED] (T2) study conducted in US. Using the same calculator, the percentage in T0 group was recalculated as 29.2% from the combined result of studies (non-Toric T0 lenses) conducted in Japan [REDACTED] [REDACTED]. Statistical test will be conducted to compare percentage of T2 with a constant of 29.2% as percentage of T0. With 30 eyes from 30 subjects in T2 group, assuming the percentage of T2 is equal to 60.9% [REDACTED], the statistical power to demonstrate superiority of T2 to T0 is 91.6% with one-sided alpha of 2.5%, using an exact test of binomial proportion.

## **13 DATA HANDLING AND ADMINISTRATIVE REQUIREMENTS**

### **13.1 Subject Confidentiality**

The Investigator must ensure that the subject's anonymity is maintained throughout the course of the study. In particular, the Investigator must keep an enrollment log with confidential identifying information that corresponds to the subject numbers and initials of each study participant. At the end of the clinical study, the Study Sponsor will collect a copy of the enrollment log *without any identifying subject information*. All documents submitted to the Study Sponsor will identify the subjects exclusively by number and demographic information. No other personally identifying information will be transmitted to the Study Sponsor.

The Study Sponsor may release anonymized study data to external researchers for purposes of future research directly related to the study objectives, or future research that is beyond the scope of the current study objectives. The Informed Consent Form explains this to study subjects. Anonymization means that all identifiable information will be removed from the dataset and all links to the subjects in the study will be removed. Anonymization of the data will maintain confidentiality of the subjects who participate in the study so that they cannot be identified by external researchers. The anonymized data set will contain records from all of the subjects in the current study, but the anonymization process might change the data set in some ways, so external researchers will be informed that they might not be able to duplicate some of the results from this study.

### **13.2 Completion of Source Documents and Case Report Forms**

The nature and location of all source documents will be identified to ensure that original data required to complete the CRFs exist and are accessible for verification by the site monitor, and all discrepancies shall be appropriately documented via the query resolution process. Site monitors are appointed by the Study Sponsor and are independent of study site staff.

If electronic records are maintained, the method of verification must be determined in advance of starting the study.

At a minimum, source documents include the following information for each subject:

- Subject identification (name, sex, race/ethnicity)
- Documentation of subject eligibility

- Date of informed consent
- Dates of visits
- Documentation that protocol specific procedures were performed
- Results of study parameters, as required by the protocol
- IP accountability records
- Documentation of AEs and other safety parameters (if applicable)
- Records regarding medical histories and the use of concomitant therapies prior to and during the study
- Date of study completion and reason for early discontinuation, if applicable

It is required that the author of an entry in the source documents be identifiable. Direct access to source documentation (medical records) must be allowed for the purpose of verifying that the data recorded on the CRF are consistent with the original source data.

Only designated individuals at the site will complete the CRFs. The CRFs must be completed at regular intervals following the clinical study visit schedule. It is expected that all data reported have corresponding entries in the source documents. The Principal Investigator is responsible for reviewing and certifying that the CRFs are accurate and complete. The only subject identifiers recorded on the CRFs will be subject number, and subject demographic information.

### **13.3 Data Review and Clarifications**

A review of CRF data to the subject's source data will be completed by the site monitor to ensure completeness and accuracy. After the CRFs have been completed, additional data clarifications and/or additions may be needed as a result of the data cleaning process. Data clarifications are documented and are part of each subject's CRF.

### **13.4 Sponsor and Monitoring Responsibilities**

The Study Sponsor will designate a monitor to conduct the appropriate site visits at the appropriate intervals according to the study monitoring plan. The clinical investigation will be monitored to ensure that the rights and well-being of the subjects are protected, the reported data are accurate, complete, and verifiable from the source documents, and the study

is conducted in compliance with the current approved protocol (and amendments[s], if applicable), with current GCP, and with applicable regulatory requirements.

The site may not screen subjects or perform the informed consent process on any subject until it receives a notification from an appropriate Study Sponsor representative that the site may commence conducting study activities. (Note: Even though routine test was operated before informed consent, these data can be use as study data.) Monitoring will be conducted periodically while the clinical study is ongoing. Monitoring methods may include site visits, telephone, e-mail, written and fax correspondence. Close-out visits will take place after the last visit of the last subject at the site.

### **13.5 Regulatory Documentation and Records Retention**

The Investigator is required to maintain up-to-date, complete regulatory documentation as indicated by the Study Sponsor and the Investigator's files will be reviewed as part of the ongoing study monitoring.

Additionally, the Investigator must keep study records and source documents consistent with the terms of the clinical study agreement with the Study Sponsor. If the Investigator retires, relocates, or for any other reason withdraws from responsibility of keeping the study records, then the Study Sponsor must be notified and suitable arrangements made for retention of study records and source documents needed to comply with national and international regulations.

At expiration of the retention period of the records, the sponsor will notify the study sites thereof.

### **13.6 Quality Assurance and Quality Control**

The Study Sponsor will secure agreement from all involved parties to ensure direct access to all study related sites, source data and documents, and reports for the purpose of monitoring and auditing by the Study Sponsor, and inspection by domestic and foreign regulatory authorities. Quality control will be applied to each stage of data handling to ensure that all data are reliable and have been processed correctly. Agreements made by the Study Sponsor with the Investigator/Institution and any other parties involved in the clinical study will be provided in writing as part of the protocol or as a separate agreement.

## 14 ETHICS

This clinical study must be conducted in accordance with the ethical principles contained within:

- The Declaration of Helsinki, and pursuant to the provisions of the protocol, Article 14 Paragraph 3 and Article 80-2 of the Pharmaceutical and Medical Device Act, the Ministerial Ordinance on Clinical Studies of Medical Devices (No. 36, Ministry of Health, Labor and Welfare, March 23, 2005) and the Notification about Enforcement of the Ministerial Ordinance on Clinical Studies of Medical Devices (No. Yakushoku-0720003, Director of Pharmaceutical and Food Safety Bureau, Ministry of Health, Labor and Welfare, July 20, 2005).
- SOPs of the Study Sponsor and contract research organizations participating in the conduct of the clinical study and all other applicable regulations.
- Notifications and timelines for reporting protocol deviations should be based upon applicable Ethics Committee requirements

The Investigator must ensure that all personnel involved in the conduct of the study are qualified to perform their assigned responsibilities through relevant education, training, and experience. The Investigator and all clinical study staff must conduct the clinical study in compliance with the protocol. Deviations from this protocol, regulatory requirements and/or GCP must be recorded and reported to the Sponsor prior to database lock. If needed, corrective and preventive action should be identified, implemented, and documented within the study records. Use of waivers to deviate from the clinical protocol is prohibited.

Before clinical study initiation, this protocol, the informed consent form, any other written information given to subjects, and any advertisements planned for subject recruitment must be approved by an IRB. Prior to the start of the study, the IRB of each study site is required to inspect and evaluate the planned study as to the acceptability of implementing the study, appropriateness of the contents of the protocol, case report form and informed consent document, and other matters related to the study from the ethical, scientific and medical points of view, with an ultimate goal of protecting the human rights and well-being of the subjects. The inspection and examination by the IRB may be performed again also during a certain period of time after the start of the study or when the head of the study site sees the necessity of additional inspection/examination so that the study may be monitored continuously. At the end of the study, the Investigator must notify the head of the investigational site about the study's completion. The IRB also must be notified if the study is terminated prematurely. Finally, the Investigator must submit the summary of progress

about clinical study to the head of the investigational site at intervals stipulated by the IRB and report it to the IRB.

Voluntary informed consent must be obtained in writing from every subject and the process shall be documented before any procedure specific to the clinical investigation is applied to the subject. The Investigator must have a defined process for obtaining consent. Specifically, the Investigator, or their delegate, must explain the clinical study to each potential subject and the subject must indicate voluntary consent by signing and dating the approved informed consent form. The subject must be provided an opportunity to ask questions of the Investigator, and if required by local regulation, other qualified personnel. The Investigator must provide the subject with a copy of the consent form written in a language the subject understands. The consent document must meet all applicable local laws and provide subjects with information regarding the purpose, procedures, requirements, and restrictions of the study, along with any known risks and potential benefits associated with the IP and the study, the available compensation, and the established provisions for maintaining confidentiality of personal, protected health information. Subjects will be told about the voluntary nature of participation in the study and must be provided with contact information for the appropriate individuals should questions or concerns arise during the study. The subject also must be told that their records may be accessed by appropriate authorities and Sponsor-designated personnel. The Investigator must keep the original, signed copy of the consent (file in subject's medical records) and must provide a duplicate copy to each subject according to local regulations.

The Study Sponsor assures that the key design elements of this protocol will be registered on [www.clinicaltrials.gov](http://www.clinicaltrials.gov) as required by current regulations and, if applicable, other public databases as required by local country regulations. In addition, results of this study will be made publicly available on [www.clinicaltrials.gov](http://www.clinicaltrials.gov) regardless of outcome as required by current regulations and, if applicable, in other public databases as required by local country regulations.

#### Specifications to secure safety of study subjects

In the event of acknowledging any adverse events, the investigator or the sub-investigator should immediately take appropriate actions irrespective of the presence or absence of causal relationship with the investigational lens.

In the case of obtaining safety-related new and significant information related to the clinical study, the sponsor should supply the information in writing to the investigator and the head of the study site and take necessary actions.

In the event of deviating from the study protocol to avoid the emergent risk and secure safety of the study subject or because of other unavoidable clinical reasons, the investigator will retain the record and submit the documentation and justification of the protocol deviation to the sponsor and the head of the study site.

#### Compensation for health hazards

If any subject has sustained health hazards arising from this study, best healthcare is provided to that subject. The Sponsor needs to be covered by insurance for liability arising from medical devices.

#### Payment to subjects

As a reward to the cooperation of each subject with the study, the Sponsor pays an amount of money, predetermined through negotiation with each participating study site, to each subject. This payment is not intended to force any subject to remain in the study.

Short Title:

**Statistical Analysis Plan
ILX140-C001**

Full Title:

**Statistical Analysis Plan
ILX140-C001 / NCT04542525**

Protocol Title:

Clinical Investigation of AcrySof IQ PanOptix Toric
Intraocular Lens Model TFNT20

[REDACTED]

[REDACTED]

Protocol TDOC Number:

TDOC-0057192

Author:

[REDACTED]

[REDACTED]

[REDACTED]

[REDACTED]

[REDACTED]

[REDACTED]

[REDACTED]

[REDACTED]

Executive Summary:

Key Objectives:

The objective of this study is to evaluate effectiveness and safety of the TFNT20 when implanted to replace the natural lens following cataract removal.

Decision Criteria for Study Success:

Primary effectiveness variable is percentage of eyes with ≤ 0.25 D refractive cylinder at Visit 3/3A (Day 30-60). The superiority of TFNT20 to non-Toric group (T0) regarding refractive cylinder is to be demonstrated when there is a statistically significant difference between the outcome in this study and the historical threshold of 29.2%.

Table of Contents

Statistical Analysis Plan ILX140-C001 1

Table of Contents 3

List of Tables..... 4

1 Study Objectives and Design..... 5

1.1 Study Objectives..... 5

1.2 Study Description 5

1.3 Randomization..... 5

1.4 Masking 5

1.5 Interim Analysis 5

2 Analysis Sets..... 6

2.1 Efficacy Analysis Sets 6

2.2 Safety Analysis Set 6

3 Subject Characteristics and Study Conduct Summaries..... 6

4 Efficacy Analysis Strategy..... 6

4.1 Efficacy Endpoints 6

4.2 Efficacy Hypotheses 7

4.3 Statistical Methods for Efficacy Analyses..... 8

4.4 Multiplicity Strategy..... 9

4.6 Interim Analysis for Efficacy 10

5 Safety Analysis Strategy..... 10

5.1 Safety Endpoints..... 10

5.2 Safety Hypotheses 10

5.3 Statistical Methods for Safety Analyses 11

5.3.1 Adverse events including secondary surgical intervention (SSI)..... 11

5.3.2 Device Deficiencies..... 12

5.3.3 Posterior Capsular Opacification..... 12

5.3.4 Posterior Capsulotomy 12

5.3.5 IOL Position Change (tilt and decentration)..... 12

5.3.6 Intraocular Pressure 12

5.3.7 Surgical Problems..... 12

5.3.8	Slit Lamp Examination.....	13
5.3.9	Dilated Fundus Examination.....	13
5.3.10	IOL Observations.....	13
5.4	Interim Analysis for Safety.....	13
6	Pharmacokinetic Analysis Strategy.....	13
7	Analysis Strategy for Other Endpoints.....	13
8	Sample Size and Power Calculations.....	14
9	References.....	14
10	Revision History.....	14

List of Tables

Table .4-1	Summary of Analysis Strategy for Key Efficacy Endpoints.....	9
------------	--	---

1 Study Objectives and Design

1.1 Study Objectives

The purpose of this study is to evaluate effectiveness and safety of the TFNT20 when implanted to replace the natural lens following cataract removal. ■■■ this is intended to confirm the safety of the test product and examine its effectiveness as a Toric lens by examining the subject's astigmatism power.

1.2 Study Description

This study is a prospective, single-center and non-comparative study. The study will include subjects must be ≥ 20 years of age with cataract who would be eligible to receive a TFNT20 lens in at least one eye based on a new Alcon Toric calculator that incorporates ocular trends in Toric IOL planning. Subject with no ocular pathology that could confound study outcome, must require clear cornea cataract extraction, and must desire an IOL that provides the potential for near, intermediate and distance vision and corrects astigmatism. Potential subjects will be screened for enrollment into this clinical trial. Those qualifying will attend a total 5 visits. If the investigational products will be implanted to both eye, the maximum number of visits is total 9 visits. Primary endpoint data will be collected at the final visit, Visit3/3A (30-60 days post implantation). No interim analysis is planned.

1.3 Randomization

This is a single-treatment study. All subjects will be implanted with AcrySof IQ PanOptix Toric Intraocular Lens Model TFNT20 unilaterally or bilaterally.

1.4 Masking

This is an open-label study. Treatment assignment may be known to the investigators, subjects or Alcon personnel involved with the planning and execution of the study.

1.5 Interim Analysis

No interim analysis is planned.

2 Analysis Sets

2.1 Efficacy Analysis Sets

All-Implanted Analysis Set (AAS)

All-Implanted Analysis Set (AAS) will include all eyes with successful test article implantation.

Best-Case Analysis Set (BAS)

Best-Case Analysis Set (BAS) will include all eyes with successful test article implantation that had

- at least 1 postoperative visit;
- no macular degeneration at any time; and
- no major protocol violation

2.2 Safety Analysis Set

The treatment-emergent safety analysis set will include all eyes with attempted implantation with the test article (successful or aborted after contact with the eye).

3 Subject Characteristics and Study Conduct Summaries

For all analysis datasets (Safety Analysis Set, AAS and BAS), demographics (sex, age [<60 , $60-69$, $70-79$, ≥ 80 years], systemic complication [None/Yes, details] and past ocular surgery [None/Yes, details]) will be summarized with the number and percent of subjects in each category for the variable. Age will also be summarized with descriptive statistics (mean, standard deviation, number of subjects or eyes, median, min and max).

4 Efficacy Analysis Strategy

4.1 Efficacy Endpoints

[figure not shown]
The followings are efficacy endpoints for this study. Absolute value will be used for evaluating primary endpoint and secondary endpoints.

Primary Endpoint

- Percentage of eyes with ≤ 0.25 D absolute refractive cylinder at Visit 3/3A (Day 30-60)

Secondary Endpoints

- Percentage of eyes with ≤ 0.5 D absolute refractive cylinder at Visit 3/3A (Day 30-60)
- Average absolute manifest refractive cylinder at Visit 3/3A (Day 30-60)

4.2 Efficacy Hypotheses

The primary analysis will be performed using an exact test of binomial proportion (one-sided alpha = 2.5%). The null (H_0) and alternative (H_1) hypotheses are;

$$H_0: \pi(T2) = 29.2\%$$

[figure not shown]
$$H_1: \pi(T2) > 29.2\%$$

, where $\pi(T2)$ is the population proportion of eyes with ≤ 0.25 D refractive cylinder at Visit 3/3A (Day 30-60) for TFNT20 (T2 hereafter) group. The 29.2% is the percentage of non-Toric (T0, hereafter) group estimated from historically combined studies [REDACTED] that would have qualified for T2 according to the new Alcon Toric calculator.

For secondary effectiveness analyses [REDACTED], no confirmatory statistical hypothesis testing will be conducted.

4.3 Statistical Methods for Efficacy Analyses

All eligible eyes will be used for the analysis. For unilaterally implanted subjects, only the eligible eye, for bilaterally implanted subjects, both eyes will be used for the analysis. The superiority of T2 to T0 regarding refractive cylinder is to be demonstrated when there is a statistically significant difference between the outcome in this study and the historical threshold of 29.2%. [REDACTED]

Secondary effectiveness variables [REDACTED] will be summarized descriptively. For continuous variables, descriptive statistics (mean, standard deviation, N, median, min and max) will be provided for actual value and change from baseline at each visit. For categorical variables, N and percent will be provided for each category at each visit. Any additional p-values from t-statistics or chi-square type statistics will be provided accordingly only for descriptive purpose. Also, a patient data listings will be provided for all effectiveness analysis data with all eyes at all visits.

Table 4-1 summarizes the key efficacy analyses.

Table 4-1 Summary of Analysis Strategy for Key Efficacy Endpoints

[figure not shown]
Endpoint	Main [REDACTED] Approach ^a	Statistical Method	Analysis Set	Missing Data Approach
Primary				
Percentage of eyes with ≤ 0.25 D refractive cylinder at Visit 3/3A	M	Exact test of binomial proportion	AAS	Observed data only

Secondary				
Percentage of eyes with ≤ 0.5 D refractive cylinder at Visit 3/3A	M	Descriptive statistics	AAS	Observed data only

Average manifest refractive cylinder at Visit 3/3A	M	Descriptive statistics	AAS	Observed data only
--	---	------------------------	-----	--------------------

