## 8 STUDY POPULATION

The study population includes approximately 30 subjects to be enrolled at 1 site.

To participate in the clinical trial, subjects must be  $\geq 20$  years of age with cataract who would be eligible to receive a TFNT20 lens in at least one eye based on a new Alcon Toric calculator that incorporates ocular trends in Toric IOL planning. Subject with no ocular pathology that could confound study outcome, must require clear cornea cataract extraction, and must desire an IOL that provides the potential for near, intermediate and distance vision and corrects astigmatism. Additional entry criteria are listed below in Sections 8.1 through 8.3.

Check all entry criteria at baseline (Visit 0/0A) and at both surgical visits (Visit 00/00A).

If the implantation was aborted and the IOL did **not** touch the eye, then the subject is required to discontinue from the study and standard of care for IOL implantation is followed. Refer to Section 10.3 Discontinued Subjects for further details. If the implantation was aborted and the IOL did touch the eye, then the subject is followed for safety evaluation on this eye only.

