### 8.1 Inclusion Criteria

Written informed consent must be obtained before any study specific assessment is performed. Upon signing informed consent, the subject is considered enrolled in the study.

Subjects eligible for inclusion in this study must fulfill **all** of the following criteria: Among the criteria listed below, ocular criteria relates to the study eye only.

1. Adults, 20 years of age or older at the time of informed consent for participating in this study, of either gender, Japanese patient diagnosed with age-related cataract.
2. Planned routine cataract surgery (need determined by the expert opinion of the investigator).
3. Eligible to be implanted with the TFNT20 as determined by a new Alcon Toric calculator in at least one eye that incorporates ocular trends in surgical planning.
4. To qualify for fellow eye implant with TFNT20, subject must have no clinically significant findings at the Visit 1 examination of the first implanted eye.

Note: This criterion only applies to subjects who are eligible for both eyes and wishes to be implanted into fellow eye with TFNT20.

5. Willing and able to complete all required postoperative visits.
6. Subjects for able to comprehend and sign the informed consent form for participating in this study.  
For the subjects who are eligible for both eyes and wishes to be implanted into fellow eye with TFNT20, subject has to comprehend and sign the informed consent form for the second eye surgery and the study examinations prior to the examinations at Visit 0A.
7. Clear intraocular media other than cataract.
8. Subjects for whom postoperative emmetropia is planned (spherical equivalent  $\pm$  0.50 D).
9. Potential postoperative BCDVA of 0.5 decimal or better.

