#### 12.4.1.2 Analysis Methods

All eligible eyes will be used for the analysis. For unilaterally implanted subjects, only the eligible eye, for bilaterally implanted subjects, both eyes will be used for the analysis. The superiority of T2 to T0 regarding refractive cylinder is to be demonstrated when there is a statistically significant difference between the outcome in this study and the historical threshold of 29.2%.

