5.4 Interim Analysis for Safety

No interim analysis is planned.

6 Pharmacokinetic Analysis Strategy

Not Applicable.

7 Analysis Strategy for Other Endpoints

Not Applicable.

8 Sample Size and Power Calculations

To enroll more than or equal to 30 eligible T2 eyes used for analysis, at least 30 subjects will be evaluated by a new Alcon Toric calculator and unilaterally or bilaterally implanted with the AcrySof IQ PanOptix IOL (TFNT20).

Using a new Alcon calculator, percentage of eyes with ≤ 0.25 D refractive cylinder at Visit 3/3A (Day 30-60) in T2 group was estimated as 60.9% based on a previous [REDACTED] (T2) study conducted in US. Using the same calculator, the percentage in T0 group was recalculated as 29.2% from the combined result of studies (non-Toric T0 lenses) conducted in Japan [REDACTED]. Statistical test will be conducted to compare percentage of T2 with a constant of 29.2% as percentage of T0. With 30 eyes from 30 subjects in T2 group, assuming the percentage of T2 is equal to 60.9% [REDACTED] the statistical power to demonstrate superiority of T2 to T0 is 91.6% with one-sided alpha of 2.5%, using an exact test of binomial proportion.

9 References

No references.

10 Revision History

This is the original (Version 1.0) Statistical Analysis Plan for this study. This version of the Statistical Analysis Plan is based on Version 2.0 of the study protocol.

Signature Page for V-CLN-0002915 v1.0

Signature Page for V-CLN-0002915 v1.0

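### The primary exact binomial test treats both eyes of a bilateral subject as independent, so the one-sided 2.5% is not guaranteed if fellow eyes are positively correlated

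*SAP*

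**What the plan says.** SAP 4.2 and Protocol 12.4.1.1 set one confirmatory hypothesis. The proportion of eyes with refractive cylinder of 0.25 D or less at Visit 3/3A is tested against a fixed historical 29.2%, by exact binomial test at one-sided 2.5%. Table 4-1 of the SAP lists this as the main approach, on the All-Implanted Analysis Set, which is a set of eyes, with observed data only.

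SAP 4.3 fixes what enters the test: "For unilaterally implanted subjects, only the eligible eye, for bilaterally implanted subjects, both eyes will be used for the analysis". Protocol 12.4.1.2 has the same rule: "for bilaterally implanted subjects, both eyes will be used for the analysis".

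Bilateral implantation is part of the design. SAP 1.3: "All subjects will be implanted with AcrySof IQ PanOptix Toric Intraocular Lens Model TFNT20 unilaterally or bilaterally". Protocol 8.1 restricts it: "To qualify for fellow eye implant with TFNT20, subject must have no clinically significant findings at the Visit 1 examination" of the first eye. The fellow eye must also be eligible, and the subject must want the second implant and consent again. The visible text sets no maximum number of bilateral subjects.

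The power statement in Protocol 12.8 rests on one eye per subject: "With 30 eyes from 30 subjects in T2 group". SAP 8 repeats it, alongside a recruitment rule that allows either pattern: "at least 30 subjects will be evaluated by a new Alcon Toric calculator and unilaterally or bilaterally implanted". Protocol 8 plans for about 30 subjects at one site.

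**The concern.** An exact binomial test has its stated size only if the outcomes counted are independent. Two eyes of one person share that person's healing, corneal anatomy and measurement conditions, so positive correlation is plausible. Each bilateral subject then adds less information than two separate eyes. The count of successes varies more than the binomial allows, and its upper tail is heavier than the cut-off assumes.

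This is the trial's only confirmatory test and its only success criterion. As visibly written, its true one-sided error can lie on either side of 2.5%, depending on how many subjects turn out to be bilateral and how strongly their eyes agree. No visible rule set in advance keeps it at or below 2.5%.

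**Working it through.** **Inputs.** Null proportion 29.2%, assumed proportion 60.9%, one-sided 2.5%, exact binomial, 30 eyes from 30 subjects, stated power 91.6% (Protocol 12.8, SAP 8). The number of bilateral subjects, m, and the within-pair correlation, ρ, are not given. Both are assumptions here, varied over a range.

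**The plan's own figure.** The smallest k with P(Bin(30, 0.292) ≥ k) ≤ 0.025 is k = 15. Its alpha is 1.31%, and power at 60.9% is 91.9%. This agrees closely with the stated 91.6%. A normal approximation gives 95.8%, so the stated figure comes from the exact test with one eye per subject.

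**True alpha with both eyes counted.** Take 30 subjects and n = 30 + m eyes. Keep the planned cut-off k for n eyes. Treat each single eye as Bernoulli(p) and each pair as

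- P(2 successes) = p² + ρpq
- P(1 success) = 2pq(1 − ρ)
- P(0 successes) = q² + ρpq

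with p = 0.292 and q = 0.708, so pq = 0.2067. For ρ = 0.3 these are 0.1473, 0.2894 and 0.5633. Convolving 30 − m single eyes with m pairs gives the exact distribution of the success count:

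| Bilateral of 30 | Eyes | Cut-off | ρ = 0 | ρ = 0.1 | ρ = 0.3 | ρ = 0.5 |
|---|---|---|---|---|---|---|
| 0 | 30 | 15 | 1.31% | 1.31% | 1.31% | 1.31% |
| 4 | 34 | 16 | 2.08% | 2.21% | 2.47% | 2.73% |
| 10 | 40 | 18 | 2.45% | 2.75% | 3.36% | 3.96% |
| 13 | 43 | 20 | 1.21% | 1.44% | 1.94% | 2.45% |
| 15 | 45 | 20 | 2.13% | 2.50% | 3.24% | 3.99% |
| 24 (worst) | 54 | 23 | 2.47% | 3.00% | 4.07% | 5.12% |
| 30 | 60 | 26 | 1.38% | 1.80% | 2.70% | 3.63% |

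**How often 2.5% is passed.** Over the 31 possible counts (0 to 30 bilateral), alpha exceeds 2.5% at 6 counts for ρ = 0.1, 12 for ρ = 0.2, 19 for ρ = 0.3 and 23 for ρ = 0.5. The smallest ρ that breaches it is 0.006 with 24 bilateral, 0.016 with 10, 0.101 with 15, 0.257 with 30, 0.324 with 4 and 0.518 with 13. With 0, 1, 2, 3 or 5 bilateral, no correlation breaches it.

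**Sensitivity.** With 28 to 34 evaluable subjects, the highest alpha over all bilateral counts is 2.9–3.0%, 3.9–4.2% and 4.9–5.3% at ρ = 0.1, 0.3 and 0.5. If the two eyes of a pair differ by 20 points around 29.2%, the row for 24 bilateral becomes 2.7%, 3.7% and 4.7%.

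**Consequence for a result.** For ρ from 0.1 to 0.7, the smallest cut-off that restores alpha to 2.5% is 0, 1 or 2 eyes above the planned one. Where they differ, the chance at a true 60.9% of landing between them is 0.2–4.6%.

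**Power.** With 30 subjects, extra eyes raise power: 94.8–99.6% with 6 to 30 bilateral and ρ of 0.3 to 0.7. Power is not the problem.

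**The case against.** The case against giving this much weight has four parts.

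- **It is conditional.** At ρ = 0.1, 25 of 31 bilateral counts stay within 2.5%. The counts 24 and 10 have the lowest breach thresholds because their binomial alpha is already 2.47% and 2.45%. This is right, and it is why the claim is loss of guaranteed control and not certain inflation.
- **Few subjects may be bilateral.** Protocol 8.1 restricts second-eye entry, and with 0 to 6 bilateral of 30 and ρ up to 0.3 the highest alpha is 2.47%. But nothing visible caps the number, and both documents provide a nine-visit schedule for bilateral subjects.
- **Redacted text may deal with it.** A redaction follows the superiority sentence in SAP 4.3, part of a Table 4-1 column header is blacked out, and no section 4.5 is visible. A supportive analysis may sit there, so absence can be stated only for visible text. The visible main analysis and success rule are unadjusted.
- **The remedy has a price.** One eye per subject gives 91.4% power or more with 28 to 34 evaluable subjects, but 87.6% with 27 and 81.3% with 24. That is true, but the sponsor's own sizing has the same sensitivity because it also counts one eye per subject.

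What stands is the limit on size and reach. With an expected gap of 29.2% to 60.9%, only a result near the cut-off would be disputed.

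**Conclusion.** The concern holds. The visible primary test does not guarantee its one-sided 2.5% when bilateral subjects are included and fellow eyes are positively correlated. With 30 evaluable subjects, a true rate of 29.2% per eye and ρ between 0.1 and 0.5, alpha ranges from below 2.5% at many bilateral counts to 5.12% at the worst. Confidence is high on the loss of control and low on the amount, because bilateral count and correlation are both assumed. The plan should be corrected because this is the sole confirmatory test and correction is cheap, although the result would probably be the same either way.

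**What to change.** Amend SAP 4.3 and Protocol 12.4.1.2 before any Visit 3/3A data are seen.

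**Preferred.** Keep the exact binomial test but count one eye per subject. Use the implanted eye for unilateral subjects. For bilateral subjects, use an eye from a random list made in advance, with the fellow eye substituted if the chosen eye has no Visit 3/3A refraction. Do not default to the first eye: Protocol 9.3 makes it the one with the smaller anticipated residual astigmatism, which would favour success. Report the all-eyes percentage as supportive, with a subject-clustered interval. With 30 subjects this gives a cut-off of 15, alpha 1.3% and power 91.9% whatever the correlation. With 28 to 34 subjects, alpha is 1.05–2.32% and power 91.4–96.5%.

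**Acceptable alternative.** Keep all eyes and divide n by a subject-clustered design effect floored at 1, then take the exact binomial tail in its beta form at that effective sample size. By enumeration for 30 subjects, all bilateral counts and ρ from 0 to 0.9, alpha is 1.05–2.16%.

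**Cost.** Wording only, with no extra subjects. One eye per subject gives up the power gained from second eyes, makes the result depend on one draw, and replaces the eye-weighted proportion of SAP 4.2 with a subject-weighted one. If bilateral and unilateral subjects differ by 10 points while the eye-weighted rate is 29.2%, its alpha is 0.7–2.1% (10, 15 or 24 bilateral), still under 2.5%. The alternative keeps eye weighting but is harder to explain, and its power with 30 subjects can fall to 90.5% at ρ = 0.7 and 88.9% at ρ = 0.9.
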